10.1.5 Pharmacokinetic analysis set

- The Pharmacokinetic Analysis Set (PAS) consists of all patients who have at least one PK blood sample providing measurable LTT462 and who satisfy the bullets below: Patient received at least one dose of study treatment
- Patient followed the dosing recommendation ([Section 6.1.1](#)) and took the drug 1 hour before or 2 hours after the meal

- Patient did not vomit within 4 hours of dose administration
- Patient provided at least one primary PK parameter

[figure not shown]

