Patients who do not experience a DLT during the first 28 days of dosing are considered to have sufficient safety evaluations if they have been observed for 28 days or more following the first dose, and are considered by both Novartis and Investigators (at the dose escalation meetings) to have enough safety data to conclude that a DLT did not occur.

PK analysis set for the treatment period

The Pharmacokinetic Analysis Set (PAS) includes all patients who have at least one PK blood sample providing measurable LTT462 and who satisfy the bullets below:

- received at least one dose of LTT462,
- patient provided at least one primary PK parameters,
- patient did not vomit within 4 hr of dose administration,

The PAS will be used for summaries of PK data (tables and figures) as well as for listings of derived parameters.

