2.3.1 Exclusion from analysis sets

In general, a patient must have provided written informed consent before inclusion into any analysis set, as specified in section 5.2 of the study protocol.

Table 2-2Reasons for excluding a patient from an analysis set

Analysis set	Deviation
Full analysis	Patient did not receive at least one dose of LTT462
Safety	Patient did not receive at least one dose of LTT462.
	Patient without at least one post-baseline safety assessment.

Novartis SAP	Confidential 13-May-2019 (11:03)	Page 10 CLTT462X2101
Analysis set	Deviation	
Dose-determining	Patient did not experience a DLT, however, the re exposure to the planned study treatment was not	
PK analysis,	If any of the conditions detailed above are violate from PAS	d, patient will be exclude

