2.13.1 Data handling principles

All concentrations below the lower limit of quantitation (LLOQ) or missing data will be labeled as such in the concentration data listings. Concentrations below the LLOQ will be treated as zero in summary statistics and for the calculation of pharmacokinetic parameters, unless otherwise stated under the Pharmacokinetic Analysis Set.

At the time of analysis, concentration data from patients may be removed from the estimation of certain PK parameters depending on the number of available blood samples, concomitant medications, vomiting, etc. Specific time points might be removed from the analysis, if technical issues with the sample are reported (e.g. sampling issues, missing information). These patients and concentration data points will be identified at the time of analysis.

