2.13.2 Data analysis set

All pharmacokinetic data analyses and PK summary statistics will be based on PAS. Only PK blood samples with date and time and for which the last prior dose dates and times are adequately recorded will be included in the PK analyses.

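### The PK analysis set excludes the whole patient for vomiting within 4 hours of a dose, so an unaffected PK profile is lost along with the affected one

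*SAP*

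**What the plan says.** The unit of the PAS is the patient. SAP section 2.3 states that it "includes all patients who have at least one PK blood sample providing measurable LTT462 and who satisfy the bullets below", and one of those bullets is "patient did not vomit within 4 hr of dose administration". Protocol section 10.1.5 words the condition almost identically: "Patient did not vomit within 4 hours of dose administration". No dose, sampling day or profile is attached in either place.

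SAP Table 2-2 (section 2.3.1) gives the consequence. Its PK row, broken in the extracted text, begins "If any of the conditions detailed above are violate" and ends with the patient being excluded from the PAS.

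The PAS governs the PK reporting. SAP section 2.3: "The PAS will be used for summaries of PK data (tables and figures) as well as for listings of derived parameters". SAP section 2.13.2: "All pharmacokinetic data analyses and PK summary statistics will be based on PAS".

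A second, finer rule sits in SAP section 2.13.1, with the same text in protocol section 10.5.3.1. At the time of analysis, "concentration data from patients may be removed from the estimation of certain PK parameters", and vomiting is one of the listed reasons.

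**The concern.** Each patient contributes more than one PK occasion: protocol section 7.2.3 plans both single-dose and steady-state characterisation. Protocol section 2.2 omits the C1D2 dose so that 48 hours can be sampled after C1D1, to obtain AUCinf and half-life. SAP section 2.13.4 then uses AUCinf and Cmax for dose proportionality.

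Vomiting after a dose can compromise the profile that follows that dose. It cannot alter a profile completed two weeks earlier. A patient-level exclusion discards both, with no pharmacokinetic reason for dropping the earlier one. The patients who lose data are, by construction, those who vomit. PK is a secondary objective and one of the inputs to the choice of dose for expansion (protocol sections 4.1.1 and 6.2.3.2). With an escalation part of at least 21 patients spread over several dose levels, each complete Day 1 profile counts.

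**Working it through.** The plan states no figure for the PAS or for vomiting, so there is nothing to reproduce. The check has two parts.

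**1. Do the rules allow a patient to keep an unaffected profile?**

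- SAP 2.3 and protocol 10.1.5: the condition is on the patient, and no dose is named.
- SAP Table 2-2: any failed condition puts the patient outside the PAS.
- SAP 2.13.2: all PK analyses and summary statistics use the PAS.
- SAP 2.13.1 and protocol 10.5.3.1: discretionary removal of concentrations from certain parameters. This can only take further data away from patients already in the PAS. It does not bring back a patient excluded under Table 2-2.

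Read together, the answer is no.

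**2. How much is lost? (illustration)**

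Inputs:

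- k = 2 profile days. Day 1 and Day 15 are the days compared for time-dependency in protocol section 10.5.3.4.
- p = probability of vomiting within 4 hours on a profile day. This is an assumption; the documents give no rate. Range taken: 2%, 5%, 10%.
- Independence between the two days, also an assumption.
- 21 patients, the minimum expected in escalation (SAP section 4.1).

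Formulas:

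- Patient-level rule, share of patients (and so of profiles) lost: 1 − (1 − p)²
- Profile-level rule, share of profiles lost: p
- Clean profiles discarded, the difference: p(1 − p)

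| p | Patient-level loss | Profile-level loss | Clean profiles discarded | Expected patients excluded of 21 |
|---|---|---|---|---|
| 2% | 1 − 0.98² = 3.96% | 2% | 0.02 × 0.98 = 1.96% | 0.8 |
| 5% | 1 − 0.95² = 9.75% | 5% | 0.05 × 0.95 = 4.75% | 2.0 |
| 10% | 1 − 0.90² = 19.0% | 10% | 0.10 × 0.90 = 9.0% | 4.0 |

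So 47% to 49% of the discarded profiles would be clean (for example 9.0/19.0 = 47%).

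**Sensitivity to independence.** In general the patient-level loss is 2p − P(vomits on both days). Under independence P(both) = p². If the same patients always vomit on both days, P(both) = p and the loss is p, the same as under the profile-level rule. With positive clustering the extra loss therefore lies between 0 and p(1 − p), and the table shows the upper end of that range.

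**Parameters that need both days.** The accumulation ratio (steady-state AUCtau over Day 1 AUCtau) and the time-dependency comparison (Day 1 AUCinf with Day 15 AUCtau) are lost if either profile is lost. With two days that is 1 − (1 − p)² under both rules, so the change recovers nothing there. The recovery is in single-profile summaries and in dose proportionality.

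**The case against.** The best defence is that finer handling was intended. SAP section 2.13.1 removes data from "certain PK parameters depending on the number of available blood samples, concomitant medications, vomiting, etc". That mention of vomiting would be nearly redundant if every patient who vomited within 4 hours were already outside the PAS. This is a fair reading of intent, and it is why the point is partly one of reconciliation. It does not settle the matter, because Table 2-2 still excludes the patient and nothing in section 2.13.1 overrides it. A qualifier may also have been lost to redaction or extraction; none is visible in either document.

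Three stronger readings are tempting and are not supported.

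- **That the rule biases exposure by dose or dose proportionality.** A reader might infer that vomiting concentrates at high dose or high exposure. No visible text gives a vomiting rate or links vomiting to dose, and vomiting may come from the disease. The selection is on vomiting; its direction with respect to exposure is unknown.
- **That most patients would be lost.** Taking the wording over all 27 QD doses of Cycle 1, a 2% chance per dose would exclude 1 − 0.98²⁷ = 42% of patients. However, the protocol asks for 4-hour vomiting to be recorded with the PK data only on PK days (sections 6.1.1 and 7.2.3.1), so the rule probably operates there. Nor can a longer count of PK days be supported from the visible text: the C1D2 and C1D3 samples belong to the C1D1 profile, and the detailed PK sampling tables are not shown.
- **That all of a patient's PK data disappear.** Raw-data listings default to the full analysis set (SAP section 2.3), so concentrations can still be listed.

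The effect on dose decisions is also indirect. The dose-decision sections (protocol 6.2.3.2 and 6.2.3.3) refer to available PK information and to evaluable patients without naming the PAS. Cohorts of 1 to 6 are pooled by dose and regimen for reporting, so an analysis group can be larger than a cohort.

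**Conclusion.** The point holds for the wording. A single qualifying episode takes the patient out of every PAS-based analysis, summary and derived-parameter listing, including a profile the episode could not have affected. This conflicts with the parameter-level handling of vomiting elsewhere in both documents.

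The size is modest and rests on assumptions: two profile days, independent days and an assumed p. At p of 2% to 10% the patient-level rule loses about 4% to 19% of profiles, roughly twice the profile-level loss, and less than that if vomiting clusters in the same patients. The gain from correcting it is in single-profile parameters and dose proportionality; accumulation and time-dependency gain little. No claim about the direction of bias can be made from the documents. It should be corrected because it discards valid data in a small trial.

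**What to change.** In protocol section 10.1.5, SAP section 2.3 and SAP Table 2-2, attach the vomiting condition to the PK profile:

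- exclude the concentrations and parameters of a PK day when vomiting occurred within 4 hours of that day's dose;
- keep the patient in the PAS with any other evaluable profile.

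Align SAP section 2.13.1 and protocol section 10.5.3.1 with this, so that one rule governs vomiting in place of a patient-level exclusion and a separate discretionary one.

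The cost is small: changed wording and a profile-level exclusion flag in the PK dataset. No new data are needed, because vomiting times on PK days are already collected (protocol section 7.2.3.1). The protocol wording needs an amendment under its section 12.1 and can go with the next one. The SAP change should be made before database lock.

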2.3.1 Exclusion from analysis sets

In general, a patient must have provided written informed consent before inclusion into any analysis set, as specified in section 5.2 of the study protocol.

Table 2-2Reasons for excluding a patient from an analysis set

Analysis set	Deviation
Full analysis	Patient did not receive at least one dose of LTT462
Safety	Patient did not receive at least one dose of LTT462.
	Patient without at least one post-baseline safety assessment.

Novartis SAP	Confidential 13-May-2019 (11:03)	Page 10 CLTT462X2101
Analysis set	Deviation	
Dose-determining	Patient did not experience a DLT, however, the re exposure to the planned study treatment was not	
PK analysis,	If any of the conditions detailed above are violate from PAS	d, patient will be exclude

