7.2.2.2 Vital signs

Vital signs (including body temperature, pulse rate and blood pressure) must be performed before and at 1, 3 and 6 hours after dosing, per institutional standards on C1D1, C1D15, [REDACTED] [REDACTED]. For all other visits that coincide with PK samples, vital signs should be taken at pre-dose and 1 hour post-dose. For all other visits indicated in [Table 7-1](#), vital signs should be recorded only at pre-dose. Blood pressure and pulse rate measurements should be assessed while the patient is sitting. On the days of blood sampling for PK, the vital signs should be collected prior to the blood collection.

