10.1.2 Safety Set

The Safety Set includes all patients who received at least one dose (full or partial) of LTT462. Patients will be analyzed according to the treatment received, where treatment received is defined as:

- The treatment assigned, if it was received at least once or
- The first study treatment received, if the treatment assigned was never received.

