2.3 Analysis sets

Full Analysis Set (FAS)

The FAS will be the default to be used for all efficacy analyses. Listings of raw data will use the FAS, unless otherwise noted. It includes all patients who received at least one dose of study drug (full or partial). Patients will be classified according to the planned (i.e., assigned) treatment (dose level, regimen, _____).

Safety Set

The safety set will be the primary population for all safety related endpoints except determination of the dose-DLT relationship. It includes all patients who received at least one dose (full or partial) of study treatment. The statement that a patient did not experience an adverse event constitutes a valid safety assessment. Patients will be analyzed according to the treatment received, where treatment received is defined as:

- The treatment assigned, if it was received at least once, or
- The first study treatment received, if the treatment assigned was never received.

Dose-determining Set

The DDS consists of all patients from the safety set in the dose escalation part of the trial who either meet the following minimum exposure criterion and have sufficient safety evaluations

Novartis	Confidential	Page 9
SAP	13-May-2019 (11:03)	CLTT462X2101

during the first 28 days of dosing or discontinue earlier due to a DLT during the first 28 days of dosing. This constitutes an evaluable patient for the determination of MTD. Patients in the DDS will be identified prior to each dose escalation meeting and will be confirmed prior to database lock.

In this study, if data on AEs, vital signs, Labs, and dose administration is collected at least at study visits C1D1, C1D8 and C1D15, patient is considered as having sufficient safety evaluations. The statement that a patient did not experience an adverse event constitutes a valid safety assessment.

A patient is considered to have met the minimum exposure requirement if they have received at least 75% of the planned doses of each of the assigned combination drugs during the first cycle (the first 28 days of dosing). For all regimens proposed this equates to at least 21 of the planned 28 doses LTT462.

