2.11.1 Adverse events

Data handling

AEs will be coded and graded using the latest version of MedDRA and CTCAE, respectively, available at the time of reporting. If CTCAE grading does not exist for an AE, grades 1, 2, 3, or 4 corresponding to the severity of mild, moderate, severe, and life-threatening, respectively, will be used. CTCAE grade 5 (death) will not be used in this study. Death information will be collected during treatment, safety follow up, and post-treatment follow up.

Progression of malignancy (including fatal outcomes), if documented by use of appropriate method (for example, as per RECIST criteria for solid tumors, should not be reported as a serious adverse event.

Adverse events separate from the progression of malignancy (example, deep vein thrombosis at the time of progression or hemoptysis concurrent with finding of disease progression) will be reported as per usual guidelines used for such events with proper attribution regarding relatedness to the drug.

A patient with multiple CTCAE grades for an AE will be summarized under the maximum grade recorded for the event. A subject with multiple occurrences of an AE is counted only once in the AE category (e.g. SOC, preferred term).

The incidence of a given AE is defined as the ratio of total number of patients experiencing the given AE at least once (defined by its preferred term [PT]) divided by the total number of patients at risk (i.e. part of the safety set). The incidence of AEs will be performed on treatment-emergent events only, i.e., AE that first occurs or worsens during treatment up to 30 days following the last treatment administration. The listing of adverse events will include all events reported during the study conduct.

Reports

The following AE summaries will be produced, including maximum CTC grade 3/4, in addition to the primary analyses:

- AEs regardless of study drug relationship
- AEs suspected to be study drug related
- AEs leading to discontinuation of study drug, regardless of study drug relationship
- AEs which are not SAEs regardless of study drug relationship
- All SAEs regardless of study drug relationship
- On-treatment deaths with cause of death by preferred term
- All deaths, with cause of death by primary system organ class and preferred term

A missing AE start date will be imputed using the following logic matrix described below.

Novartis	Confidential	Page 17
SAP	13-May-2019 (11:03)	CLTT462X2101

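### SAP Table 2-2 excludes from the Safety Set a dosed patient with no post-baseline safety assessment, a condition absent from the set's definition in Protocol 10.1.2 and SAP 2.3

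*SAP*

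**What the plan says.** Both documents define the Safety Set by dosing alone. Protocol 10.1.2 states: "The Safety Set includes all patients who received at least one dose (full or partial) of LTT462". SAP 2.3 repeats the rule: "It includes all patients who received at least one dose (full or partial) of study treatment".

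SAP 2.3.1, Table 2-2, then gives two separate reasons for leaving a patient out of the Safety Set. The first matches the definitions: "Patient did not receive at least one dose of LTT462". The second does not: "Patient without at least one post-baseline safety assessment". For the Full Analysis Set (FAS), which has the same one-dose entry condition, the table gives only the first reason.

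The set carries most of the primary analysis. SAP 2.3 says: "The safety set will be the primary population for all safety related endpoints except determination of the dose-DLT relationship". SAP 2.11.1 defines adverse-event incidence as the number of patients with the event "divided by the total number of patients at risk (i.e. part of the safety set").

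**The concern.** Two statisticians working from the same SAP could build different Safety Sets, one from the definition in 2.3 and one from Table 2-2. Nothing in the legible text announces or justifies a departure from the protocol's definition.

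The extra row also makes membership depend on what happens after dosing. The patients it can remove are those for whom nothing was recorded after the first dose. Safety and tolerability are the primary objective, so a treated patient should not drop out of the safety tables because follow-up was missing.

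**Working it through.** **No figure to reproduce.** The primary safety analysis is descriptive (SAP 2.9.2), and no stated number depends on this rule. The check is a comparison of texts, followed by an illustration.

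**Step 1: compare the rules for a dosed patient with no post-dose safety data.**

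| Source | In the Safety Set? |
|---|---|
| Protocol 10.1.2 | Yes |
| SAP 2.3 | Yes |
| SAP Table 2-2, not-dosed row | Yes (the row does not apply) |
| SAP Table 2-2, no-assessment row | No |

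Reading the two table rows as jointly required would remove the conflict but leave the second row with no function. An undosed patient is already excluded, and SAP 6.1 defines baseline relative to first dosing, so such a patient can have nothing post-baseline.

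**Step 2: who can be removed.** Two provisions narrow the group.
- On the first dosing day, vital signs "must be performed before and at 1, 3 and 6 hours after dosing, per institutional standards on C1D1" (Protocol 7.2.2.2).
- SAP 2.3 says: "The statement that a patient did not experience an adverse event constitutes a valid safety assessment".

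Anyone with a recorded adverse event or DLT has an assessment and stays in. That leaves only a dosed patient with no post-dose entry of any kind.

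One case is unresolved. Grade 5 is not used, and deaths are collected on a separate Death form (Protocol 8.1.1). The same section says fatal outcomes of documented progression are not to be reported as serious adverse events. The SAP does not say whether a Death form alone is a safety assessment.

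**Step 3: which outputs are affected.**
- Adverse-event incidence and the death summaries (SAP 2.11, 2.11.1): Safety Set, so affected.
- Exposure and dose intensity (SAP 2.8, 2.8.1): Safety Set, so affected.
- Disposition (SAP 2.6): FAS, so unaffected.
- Dose-determining set (DDS): a patient with no recorded DLT needs safety data at C1D1, C1D8 and C1D15, and 28 days of observation sufficient to rule out a DLT (SAP 2.3). A patient with no post-dose data fails this already, so the DDS is unaffected.

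**Step 4: illustration.** Let n be the dosed patients in a treatment group, x those with a given event, and k those removed by the row. The documents give no k, so 1 and 2 are assumed; k = 0 is plausible and changes nothing. A removed patient has no recorded adverse event, so x is unchanged. Incidence is x/n under the definitions and x/(n − k) under Table 2-2.

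| n | k | x | x/n | x/(n − k) |
|---|---|---|---|---|
| 3 | 1 | 1 | 1/3 = 33.3% | 1/2 = 50.0% |
| 6 | 1 | 1 | 1/6 = 16.7% | 1/5 = 20.0% |
| 6 | 1 | 2 | 2/6 = 33.3% | 2/5 = 40.0% |
| 6 | 2 | 2 | 2/6 = 33.3% | 2/4 = 50.0% |
| 21 | 1 | 2 | 2/21 = 9.5% | 2/20 = 10.0% |
| 21 | 2 | 2 | 2/21 = 9.5% | 2/19 = 10.5% |

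Here 6 is the minimum number at the MTD/RDE level and 21 the expected minimum for escalation (SAP 4.1); 3 is a small group within the permitted cohort sizes. Adverse-event percentages rise. The death table moves the other way if the removed patient is the one who died: with n = 6 and one such death, 1/6 = 16.7% becomes 0/5 = 0%.

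**The case against.** The strongest reply is that the row will almost never operate. Dosing on PK sampling days is supervised in clinic (Protocol 6.1.1), C1D1 is such a day, and three sets of post-dose vital signs are scheduled. A bare no-event statement is enough, and data collected before withdrawal of consent are kept (Protocol 7.1.6). A fatal adverse event is itself a serious adverse event, reportable within 24 hours (Protocol 8.2.1, 8.2.2), so most early deaths would bring safety data with them. All of this stands, and it limits the size of the point.

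A second reply is that the no-event sentence sits inside SAP 2.3's Safety Set paragraph and serves a purpose only if some assessment is expected, so the row is not wholly foreign to the SAP. That is fair as far as it goes. However, the sentence says what counts as an assessment and does not make one a condition of membership. It is a reason to reconcile the text, and it does not resolve the conflict.

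A reader might infer more than the documents support:
- **That early drop-outs as a class are lost.** A patient who leaves after day 1 would normally have data and stay in.
- **That dose determination is affected.** Such a patient already fails the DDS criteria, so the model input and the MTD/RDE decision do not change.
- **That the patient vanishes from the report.** Demographics, disposition and the protocol-deviation listing use the FAS (SAP 2.5 to 2.7).
- **That single-patient cohorts make the effect extreme.** Tables pool cohorts of the same dose and regimen into treatment groups (Protocol 10, SAP 2.1). An empty group would need a dose level with only one patient ever treated, who also had no post-dose data.

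**Conclusion.** The contradiction is certain and lies in current, legible text: Table 2-2 excludes a patient whom Protocol 10.1.2 and SAP 2.3 include. Its practical effect is probably small and may be nil. It reaches only the Safety Set adverse-event, death, exposure and dose-intensity summaries, and only for a dosed patient with no post-dose safety record. The shift from 33.3% to 40.0% in a group of 6 assumes one such patient and is not a forecast. No test, sample size or dose decision depends on the row. The most awkward case is an early death from documented progression known only from the Death form. It could leave the death summaries unless the SAP says that this record counts. The point is a minor correction, worth making because the rule as written gives the wrong denominator whenever it applies.

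**What to change.** In SAP Table 2-2, delete the no-post-baseline-assessment row for the Safety Set, leaving failure to receive at least one dose of LTT462 as the only reason for exclusion. The table then agrees with Protocol 10.1.2 and SAP 2.3, and the Safety Set has the same members as the FAS. The grouping rules (treatment received for the Safety Set, treatment assigned for the FAS) stay as they are.

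Add a listing of any dosed patient without post-baseline safety data, so that a reader can see how many patients in the denominator contributed no post-dose observation. With the row gone, the question whether a Death form is an assessment no longer affects membership.

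The cost is one table row and one short listing, made by SAP amendment before database lock or addendum after it (SAP 1). No protocol change or new data collection is needed.
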